5.2 Patient Enrollment

All patients who sign an Institutional Review Board (IRB) approved Informed Consent Form (ICF) and an authorization for Protocol CLP-0001 for use of Protected Health Information (PHI) will be assigned a unique screening number consisting of a 4-digit sequential number assigned by Medrio EDC.

	DOCUMENT TITLE: A Prospective, Post-Market, Multi-Center Study Evaluating ViBone in Cervical and Lumbar Spine Fusion	DOCUMENT NUMBER: CLP-0001
--	---	-------------------------------------

6 PATIENT SELECTION

6.1 Study Population

Up to 50 ACDF and up to 50 lumbar interbody fusion patients from up to twenty centers in the United States will be enrolled. The study population will consist of male and female patients, 18-80 years of age. Eligible patients should have spondylosis, spondylolisthesis, degenerative disc disease, or herniated nucleus pulposus. Cervical fusion patients shall undergo ACDF surgery using ViBone at 1 to 3 contiguous levels between C2 and C7. Lumbar fusion patients shall undergo lumbar interbody fusion surgery using ViBone at 1 to 3 contiguous levels between L1 and S1.

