6.2 Eligibility criteria

6.2.1 Informed Consent Form

Each patient will be required to sign an IRB-approved ICF prior to enrollment in the study.

The ICF and product package insert will be used to explain the study and fully disclose known risks and benefits. Subjects will not directly benefit from being in this study; however, the results of this study may help people undergoing spine fusion in the future. As with implantation of all human allograft tissue, risks associated with the implantation of ViBone include lack of response from the recipient (e.g., lack of fusion or non-union with adjacent tissue). It is also possible for a host site to become infected or the allograft tissue may cause an inflammatory response. Current technologies may not preclude the transmission of infectious agents or disease, including hepatitis and HIV. ViBone is preserved in 5% dimethyl sulfoxide (DMSO) in a 0.9% sodium chloride solution. Povidone iodine, Dulbecco's phosphate buffered saline, sodium chloride irrigation solution, sodium phosphate, hydrochloric acid and hydrogen peroxide are all used for processing, preservation and storage of the allografts and trace amounts of these solutions may be present in the product.

There are no additional medical risks involved in participating in this study. The only additional risk from taking part in this study is that the confidentiality of subject information may be lost or compromised.

The ICF must include the elements required by the FDA in US 21 CFR 50 and International Conference on Harmonization (ICH) guidelines.

Patients will also be required to consent to the use of their PHI according to all applicable health information privacy regulations. This authorization can be part of the ICF or can be a separate document.

Each Investigator participating in the study is responsible for obtaining approval from Aziyo for any consent documents prior to their submission to their IRB and prior to their use. Each Investigator participating in the study is also responsible for ensuring that a written ICF and written authorization for use of PHI are obtained from each patient that they enroll into the study at the time of that patient's enrollment. Documentation of the informed consent process must be completed by research personnel and the patient will receive a copy of the signed ICF. No study-related activities may be performed on any patient and no data may be

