	DOCUMENT TITLE: A Prospective, Post-Market, Multi-Center Study Evaluating ViBone in Cervical and Lumbar Spine Fusion	DOCUMENT NUMBER: CLP-0001
--	---	-------------------------------------

collected from any subject for study purposes prior to receiving these consents and authorizations.

Subjects will be allowed to withdraw consent at any time for any reason.

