6.2.2 Inclusion Criteria

In order to be eligible, patients are required to meet the following inclusion criteria:

- Male or female, 18-80 years of age
- For cervical cases – ACDF surgery at 1, 2, or 3 contiguous levels between C2-C7
- For lumbar cases – lumbar interbody fusion surgery at 1, 2, or 3 contiguous levels between L1-S1
- Patient signed Informed Consent Form with HIPAA Authorization
- Appropriate candidate for surgery
- Patient will adhere to the scheduled follow-up visits and requirements of the protocol
 - Routine patient exams include pre-operative, operative, and at least two post-operative visits (6 and 12 months post-surgery)
 - Pre-operative and post-operative visits include radiological examination (X-ray (required) and CT scan (if available))

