6.2.3 Exclusion Criteria

Patients are excluded if any of the following exclusion criteria are met prior to undergoing surgery:

- Long term use of medications that are known to inhibit fusion or bone metabolism or immune suppressants 6 months prior to surgery (i.e., steroids, chemotherapy, DMARDs, etc.)
- Treatment with radiotherapy Both cervical and lumbar fusion during the same procedure
- Acute or chronic systemic or localized spinal infections
- Instability associated with major reconstructive surgery for primary tumors or metastatic malignant tumors of the cervical (for ACDF patients) or lumbar (for TLIF, PLIF, LLIF, and ALIF patients) spine
- Previous pseudoarthrosis at any level of the cervical (for ACDF patients) or lumbar (for TLIF, PLIF, LLIF, and ALIF patients) spine
- Nursing mothers or women who are pregnant or plan to become pregnant during the course of the study

	DOCUMENT TITLE: A Prospective, Post-Market, Multi-Center Study Evaluating ViBone in Cervical and Lumbar Spine Fusion	DOCUMENT NUMBER: CLP-0001
--	--	-------------------------------------

- Current or recent history of malignancy or infectious disease. Patients with current or recent history of basal cell carcinoma are eligible.
- Inability to provide informed consent
- Rapid joint disease, bone absorption, osteomalacia, and/or diagnosed osteoporosis (bone density test score of ≤ -2.5).
- Other medical or surgical conditions which would preclude the potential benefit of surgery, such as congenital abnormalities, immunosuppressive disease, elevation of sedimentation rate unexplained by other diseases, elevation of white blood count (WBC), or marked left shift in the WBC differential count.
- Active local or systemic infection or is undergoing adjunctive treatment for local or systemic infection.

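### Selection on prognosis before consent is neither restricted nor measured, although fusion rates are to be set against external data

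*Combined protocol and SAP*

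**What the plan says.** Section 6.1 (Study Population) gives maximum cohort sizes and a maximum number of centers: "Up to 50 ACDF and up to 50 lumbar interbody fusion patients from up to twenty centers in the United States will be enrolled". It sets no minimum, no site quota and no rule on which eligible patients are to be approached.

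Under section 5.2 (Patient Enrollment), a patient who has signed the consent form and the health-information authorization "will be assigned a unique screening number consisting of a 4-digit sequential number assigned by Medrio EDC". The close-out in section 7.2.4 covers enrolled patients, including those given an ID but not treated and those who leave early. The code list in section 16.1 covers enrolled subjects.

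Section 6.2.1 puts consent first: "No study-related activities may be performed on any patient and no data may be" (the sentence runs over the page) "collected from any subject for study purposes prior to receiving these consents and authorizations".

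Some entry criteria call for site judgment. Section 6.2.2 includes "Appropriate candidate for surgery" and "Patient will adhere to the scheduled follow-up visits and requirements of the protocol". Section 6.2.3 has an open-ended exclusion that begins "Other medical or surgical conditions which would preclude the potential benefit of surgery".

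Sections 4.2, 5.1, 10 and 16.2 plan a comparison of results with published or retrospective data on autograft or comparable grafts. Section 12 makes the statistics descriptive, with confidence intervals for surgical outcomes and a summary of baseline variables.

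**The concern.** In a single-arm study read against outside data, who is enrolled feeds directly into the comparison. Eligibility is wide: ages 18 to 80, four diagnoses, one to three levels, and several lumbar approaches. If patients with a better outlook for fusion are more likely to be approached, the observed rate rises for reasons unrelated to the graft, and the difference may be read as a graft effect.

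The confidence intervals in section 12 describe sampling error and do not cover this. Nor can the analysis correct for it afterwards if neither the number nor the type of eligible patients left out was recorded.

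**Working it through.** The plan gives no assumed fusion rate, margin or power for this point, so there is no figure of its own to reproduce. The check has two parts.

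**1. Where study records begin**

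| Step | Plan | Covers eligible patients not enrolled? |
|---|---|---|
| Approach to patients | No consecutive-offer or sampling rule found | No |
| Numbering | After consent and authorization (5.2) | No |
| Close-out | Enrolled or ID-assigned patients (7.2.4) | No |
| Site list | Enrolled subjects (16.1) | No |
| Monitoring | Optional; concerned with satisfactory recruitment (7.3) | Not required |
| Baseline summary | Case mix of those enrolled (12) | No |

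Selection before consent is thus neither restricted nor counted.

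**2. What selection could do**

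In general, bias = (1 − c) × (rate in enrolled − rate in not enrolled), where c is the fraction of eligible patients enrolled. The plan collects neither c nor the rate in those not enrolled, so study data cannot bound the bias.

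*Illustration A. All inputs are assumed; none is in the documents.* The higher-risk share is 0.30 with 70% fusion, and the others have 91.4%, chosen to give 85% overall.

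- All eligible enrolled: 0.30 × 0.70 + 0.70 × 0.914 = 0.850.
- Half of the higher-risk group not approached: their share becomes 0.15/0.85 = 17.6%, and the rate is (0.15 × 0.70 + 0.70 × 0.914)/0.85 = 0.876, or +2.6 points. The general formula agrees: 0.15 × (0.876 − 0.70) = 0.026.
- None of the higher-risk group approached: 91.4%, or +6.4 points.

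*Illustration B. Other assumed inputs.* Let f be the favorable share of eligible patients, pF and pU the fusion rates in favorable and unfavorable cases, and r the enrollment probability of unfavorable relative to favorable cases. Then fe = f/(f + (1 − f)r), and the enrolled rate is fe × pF + (1 − fe) × pU.

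| pF, pU, f | True rate | r = 1/2 | r = 1/4 | r = 0 |
|---|---|---|---|---|
| 95%, 75%, 0.5 | 85.0% | 88.3% (+3.3) | 91.0% (+6.0) | 95.0% (+10.0) |
| 95%, 80%, 0.6 | 89.0% | 91.2% (+2.2) | 92.9% (+3.9) | 95.0% (+6.0) |
| 90%, 70%, 0.6 | 82.0% | 85.0% (+3.0) | 87.1% (+5.1) | 90.0% (+8.0) |

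Across these scenarios the bias runs from +2.2 to +10.0 points. The top of the range requires that no unfavorable case is enrolled anywhere.

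*Against sampling error.* At n = 50 and 85%, the approximate 95% half-width is 1.96 × √(0.85 × 0.15/50) = 0.099, about 10 points. With a true rate of 85%, the chance that an exact (Clopper-Pearson) 95% interval lies wholly above 85% is 1.4% without selection, 5.8% if the enrolled rate is 88.3%, and 16.1% if it is 91%. Moderate selection is therefore smaller than the sampling error of one cohort, but it is systematic.

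**The case against.** The strongest reply is that this is a descriptive post-market registry with no test, margin or decision rule, and that an external comparison is weak with or without a log. That is fair, and it keeps the point minor. It does not remove it, because the comparison is planned in four sections and a tally would help a reader judge it.

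Four stronger readings are tempting, and the documents do not support them.

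- *Sites are permitted to pick cases.* No section says so; this would be an inference from silence. Appendices 1 and 2 (the investigator agreement and the sample consent form) were not in the text available for review and could not be checked for enrollment terms.
- *Selection is invisible altogether.* Consent and eligibility precede surgery, so cases cannot be picked on observed outcome. Sequential EDC numbers and close-out make losses after consent visible. Baseline and surgical data (7.2.1, 7.2.2) show the case mix enrolled. The package insert (Appendix 4) requires recipient records for allografts, so a site count of ViBone recipients exists in principle, although it is not a study record of eligible patients.
- *Each site enrolls so few that choosing is easy.* The average of 50/20 = 2.5 per cohort per center needs all 20 centers to take part equally. Section 5.1 also expects about 200 subjects, while the caps sum to 100. The two must be reconciled, and at 200 split equally the average would be 5.
- *The judgment-based criteria license skipping patients.* Being a suitable surgical candidate separates little among people already having the operation, and the adherence criterion is tied to stated visits and imaging. The criteria leave some room for judgment but do not show that eligible patients may be passed over.

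The direction is also unproven: a site could enroll harder cases, which would bias the rate downward.

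**Conclusion.** The point holds for selection before consent. The reviewed text neither requires consecutive offers nor counts eligible patients who were not enrolled, and the results will be compared with outside data without a concurrent control. The size of any bias is unknown. Under the assumed rates, partial selection moves the fusion rate by a few points; larger shifts need near-complete omission of unfavorable cases. This is a low-severity weakness that is cheap to reduce. It is not evidence that the fusion rate will be inflated.

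**What to change.** In section 5.2, require each site to offer enrollment to consecutive eligible patients scheduled for ACDF or lumbar interbody fusion with ViBone for as long as that cohort is open at the site. This wording avoids a per-site allotment, which the plan does not define. Keep a de-identified tally of eligible patients not enrolled: count, cohort, and a broad reason such as not approached or declined. Report the enrolled fraction by center beside the fusion rates.

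Add a matching sentence in section 6.2.1, subject to IRB agreement, stating that this tally is allowed despite the bar on collecting data before consent.

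The cost is two short text changes, IRB agreement and a small burden at each site. The tally should start with enrollment, since it cannot be rebuilt reliably later. It does not address selection in who receives ViBone at all, which should be stated as a limitation when the results are compared with other grafts.

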6.2 Eligibility criteria

6.2.1 Informed Consent Form

Each patient will be required to sign an IRB-approved ICF prior to enrollment in the study.

The ICF and product package insert will be used to explain the study and fully disclose known risks and benefits. Subjects will not directly benefit from being in this study; however, the results of this study may help people undergoing spine fusion in the future. As with implantation of all human allograft tissue, risks associated with the implantation of ViBone include lack of response from the recipient (e.g., lack of fusion or non-union with adjacent tissue). It is also possible for a host site to become infected or the allograft tissue may cause an inflammatory response. Current technologies may not preclude the transmission of infectious agents or disease, including hepatitis and HIV. ViBone is preserved in 5% dimethyl sulfoxide (DMSO) in a 0.9% sodium chloride solution. Povidone iodine, Dulbecco's phosphate buffered saline, sodium chloride irrigation solution, sodium phosphate, hydrochloric acid and hydrogen peroxide are all used for processing, preservation and storage of the allografts and trace amounts of these solutions may be present in the product.

There are no additional medical risks involved in participating in this study. The only additional risk from taking part in this study is that the confidentiality of subject information may be lost or compromised.

The ICF must include the elements required by the FDA in US 21 CFR 50 and International Conference on Harmonization (ICH) guidelines.

Patients will also be required to consent to the use of their PHI according to all applicable health information privacy regulations. This authorization can be part of the ICF or can be a separate document.

Each Investigator participating in the study is responsible for obtaining approval from Aziyo for any consent documents prior to their submission to their IRB and prior to their use. Each Investigator participating in the study is also responsible for ensuring that a written ICF and written authorization for use of PHI are obtained from each patient that they enroll into the study at the time of that patient's enrollment. Documentation of the informed consent process must be completed by research personnel and the patient will receive a copy of the signed ICF. No study-related activities may be performed on any patient and no data may be

	DOCUMENT TITLE: A Prospective, Post-Market, Multi-Center Study Evaluating ViBone in Cervical and Lumbar Spine Fusion	DOCUMENT NUMBER: CLP-0001
--	---	-------------------------------------

collected from any subject for study purposes prior to receiving these consents and authorizations.

Subjects will be allowed to withdraw consent at any time for any reason.

6.2.2 Inclusion Criteria

In order to be eligible, patients are required to meet the following inclusion criteria:

- Male or female, 18-80 years of age
- For cervical cases – ACDF surgery at 1, 2, or 3 contiguous levels between C2-C7
- For lumbar cases – lumbar interbody fusion surgery at 1, 2, or 3 contiguous levels between L1-S1
- Patient signed Informed Consent Form with HIPAA Authorization
- Appropriate candidate for surgery
- Patient will adhere to the scheduled follow-up visits and requirements of the protocol
 - Routine patient exams include pre-operative, operative, and at least two post-operative visits (6 and 12 months post-surgery)
 - Pre-operative and post-operative visits include radiological examination (X-ray (required) and CT scan (if available))

6.2.3 Exclusion Criteria

Patients are excluded if any of the following exclusion criteria are met prior to undergoing surgery:

- Long term use of medications that are known to inhibit fusion or bone metabolism or immune suppressants 6 months prior to surgery (i.e., steroids, chemotherapy, DMARDs, etc.)
- Treatment with radiotherapy Both cervical and lumbar fusion during the same procedure
- Acute or chronic systemic or localized spinal infections
- Instability associated with major reconstructive surgery for primary tumors or metastatic malignant tumors of the cervical (for ACDF patients) or lumbar (for TLIF, PLIF, LLIF, and ALIF patients) spine
- Previous pseudoarthrosis at any level of the cervical (for ACDF patients) or lumbar (for TLIF, PLIF, LLIF, and ALIF patients) spine
- Nursing mothers or women who are pregnant or plan to become pregnant during the course of the study

	DOCUMENT TITLE: A Prospective, Post-Market, Multi-Center Study Evaluating ViBone in Cervical and Lumbar Spine Fusion	DOCUMENT NUMBER: CLP-0001
--	--	-------------------------------------

- Current or recent history of malignancy or infectious disease. Patients with current or recent history of basal cell carcinoma are eligible.
- Inability to provide informed consent
- Rapid joint disease, bone absorption, osteomalacia, and/or diagnosed osteoporosis (bone density test score of ≤ -2.5).
- Other medical or surgical conditions which would preclude the potential benefit of surgery, such as congenital abnormalities, immunosuppressive disease, elevation of sedimentation rate unexplained by other diseases, elevation of white blood count (WBC), or marked left shift in the WBC differential count.
- Active local or systemic infection or is undergoing adjunctive treatment for local or systemic infection.

7 STUDY PROCEDURES

7.1 Schedule of Assessments

Study assessments are summarized below in Table 1, and are further described in Section 7.2.

Table 1: Schedule of Assessments

	Pre-Surgery Screening Visit	Surgical Procedure Visit	Follow-Up Visits (+/- 1 Month)
Visit Window	Day -30 to 0	Day 0	6 and 12 Months Post Surgery
Inclusion/Exclusion Determination	X		
Informed Consent/PHI Authorization	X		
Baseline Demographics and Basic Patient Information	X		
Surgical Procedure Details		X	
Radiological Assessment (including flexion/extension)	X ^{1,2}		X ³
Oswestry Disability Index (Lumbar Fusion) or Neck Disability Index (Cervical Fusion)	X		X
Visual Analog Scale (Both Leg and Back Pain)	X		X
ViBone-Related Serious Adverse Reactions Assessment			As needed

¹ Baseline radiographs may be up to 12 months prior to the surgical procedure.

	DOCUMENT TITLE: A Prospective, Post-Market, Multi-Center Study Evaluating ViBone in Cervical and Lumbar Spine Fusion	DOCUMENT NUMBER: CLP-0001
--	---	-------------------------------------

² Flexion/extension x-rays are not required at baseline, but will be collected if captured.

³ Flexion/extension x-rays are required at all follow-up visits.

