Patient Population:	
Included are both male and female patients, 18-80 years of age with spondylosis, spondylolisthesis, degenerative disc disease, or herniated nucleus pulposus affecting 1, 2, or 3 contiguous levels of the spine between C2 and C7 (for cervical patients) or L1 and S1 (for lumbar patients).
 
Patients must be undergoing ACDF or lumbar interbody fusion using ViBone to be eligible for the study.

Outcome Measures:	
Primary:
 
 Incidence of successful fusion measured radiographically by 12 months post-surgery 
Secondary:
 
 Incidence of successful fusion measured radiographically by 6 months post-surgery Oswestry Disability Index (ODI)/Neck Disability Index (NDI) relative to baseline. Visual Analog Scale (VAS) relative to baseline. Incidence of subjects experiencing ViBone-related serious adverse reactions.
Duration:	Subjects will be evaluated via routine follow up visits through 12 months post-surgery.
Centers:	Up to 20 centers in the U.S.

	DOCUMENT TITLE: A Prospective, Post-Market, Multi-Center Study Evaluating ViBone in Cervical and Lumbar Spine Fusion	DOCUMENT NUMBER: CLP-0001
--	---	-------------------------------------

Study contact for discussion of protocol-specific issues:

[name]

Aziyo Biologics, Inc.

[contact]

Email: [contact]

**SAFETY REPORTING CONTACT INFORMATION:
REPORTING OF SAFETY INFORMATION TO SPONSOR**

Aziyo pharmacovigilance designee and contact information for adverse reaction reporting:

[name]

Aziyo Biologics, Inc.

[contact]

Email: [contact]

Table of Contents

1	ABBREVIATIONS	7
2	TRADEMARK STATEMENTS	8
3	INTRODUCTION	8
3.1	Spine Fusion	8
3.2	Viable Bone Allografts	8
3.3	Description of ViBone	8
4	STUDY PURPOSE AND OBJECTIVES	9
4.1	Study Purpose	9
4.2	Objectives	9
5	STUDY DESIGN	9
5.1	Design Summary	9
5.2	Patient Enrollment	9
6	PATIENT SELECTION	10
6.1	Study Population	10
6.2	Eligibility criteria	10
6.2.1	Informed Consent Form	10
6.2.2	Inclusion Criteria	11
6.2.3	Exclusion Criteria	11
7	STUDY PROCEDURES	12
7.1	Schedule of Assessments	12
7.2	Study Visits	13
7.2.1	Pre-Surgery Screening Visit	13
7.2.2	Surgical Procedure Visit	13
7.2.3	Follow-Up Visits	13
7.2.4	Subject Close-Out	14

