4.2 Objectives

Subjects will be followed for 12 months post-surgery to determine the incidence of successful fusion at 12 months postoperatively. This data will be compared to published and/or retrospective data for autograft or other similar products.

Additional study objectives include:

- Incidence of successful fusion measured radiographically at 6 months post-surgery
- Change from baseline in Oswestry Disability Index (lumbar interbody fusion patients) or Neck Disability Index (ACDF patients)
- Change from baseline in Visual Analog Scale for back and leg pain
- Incidence of ViBone-related serious adverse reactions

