7.2.1 Pre-Surgery Screening Visit

The Pre-Surgery Screening Visit may take place up to and including 30 days prior to the date of the surgical procedure. The following information shall be collected during the Pre-Surgery Screening Visit:

- Inclusion/Exclusion Determination
- Written informed consent and written authorization for use and disclosure of PHI
- Demographics (age, gender, ethnicity/race)
- Medical History
- Physical Exam, including height, and body weight
- Oswestry Disability Index (lumbar fusion) (Appendix 5) or Neck Disability Index (cervical fusion) (Appendix 6)
- Visual Analog Scale (both leg and back pain) (Appendix 7)
- Radiological Assessment – at minimum, lateral and anterior/posterior radiographs are required at baseline. Flexion and extension radiographs will also be collected if captured by the investigator. If performed, CT scans will also be collected.

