7.2.3 Follow-Up Visits

Study-related Follow-Up Visits shall occur at 6 months and 12 months (\pm 1 month) after the date of the surgical procedure. The following information shall be collected at each Follow-Up Visit:

- Surgical Complication Assessment
- Oswestry Disability Index (lumbar fusion) or Neck Disability Index (cervical fusion)
- Visual Analog Scale (both leg and back pain)
- Radiological Assessment – at minimum, lateral, anterior/posterior, flexion and extension radiographs are required at each follow-up visit. If performed, CT scans will also be collected.

	DOCUMENT TITLE: A Prospective, Post-Market, Multi-Center Study Evaluating ViBone in Cervical and Lumbar Spine Fusion	DOCUMENT NUMBER: CLP-0001
--	--	-------------------------------------

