10 OUTCOME MEASURES

The following outcome measures will be assessed at 6 months and 12 months and compared to published and/or retrospective data for autograft or other similar products:

Study objectives are to detect:

- Fusion rates as determined by radiographic imaging at 6 and 12 months post-surgery.
 - Fusion of the interbody space shall be deemed successful if the following radiographic endpoints are demonstrated on x-ray examination (lateral, anterior/posterior, flexion and extension): Evidence of bridging trabecular bone between the involved motion segments, translational motion <3mm; and angular motion <5°.¹
- Changes in Oswestry Disability Index/Neck Disability Index from baseline, at all available follow-up time-points.
- Changes in Visual Analog Scale (VAS) from baseline, at all available follow-up time-points.

Safety evaluations include:

- Incidence of ViBone-related serious adverse reactions.

	DOCUMENT TITLE: A Prospective, Post-Market, Multi-Center Study Evaluating ViBone in Cervical and Lumbar Spine Fusion	DOCUMENT NUMBER: CLP-0001
--	---	-------------------------------------

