19.6 Appendix 7: Visual Analog Scale

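### The VAS is specified as back and leg pain for both cohorts, so the cervical (ACDF) VAS change would describe regions the surgery did not treat

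*Combined protocol and SAP*

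**What the plan says.** The VAS appears as an outcome or an assessment in six readable places. Four name a body site:

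- Section 4.2 (Objectives): "Change from baseline in Visual Analog Scale for back and leg pain".
- Section 7.1, Table 1: "Visual Analog Scale (Both Leg and Back Pain", marked at screening and at the 6- and 12-month visits.
- Section 7.2.1 (screening): "Visual Analog Scale (both leg and back pain) (Appendix 7".
- Section 7.2.3 (follow-up): "Visual Analog Scale (both leg and back pain".

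Two name no site: the synopsis ("Visual Analog Scale (VAS) relative to baseline") and Section 10 ("Changes in Visual Analog Scale (VAS) from baseline, at all available follow-up time-points"). None of the six limits the VAS to lumbar subjects.

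The disability index is handled differently. Table 1 has "Oswestry Disability Index (Lumbar Fusion) or Neck Disability Index (Cervical Fusion", and 4.2, 7.2.1 and 7.2.3 make the same division by region.

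The form itself should be in Section 19.6, but only its heading, "Appendix 7: Visual Analog Scale", could be read. That is a limit of the text available for review and is not held against the plan.

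**The concern.** Section 6.1 places the cervical surgery between C2 and C7. A site that follows the visit lists literally would ask these subjects about back and leg pain, before and after surgery, and not about the region operated on.

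VAS change from baseline is a listed secondary outcome. The synopsis and Section 16.2 say the cervical and lumbar data are analysed separately, so the cervical VAS result would stand alone. Section 10 also sets the outcomes against published or retrospective data. A cervical comparison built on back and leg scores would not inform on neck or arm pain. The loss would be permanent, because a pre-surgery score that was not taken cannot be recovered afterwards.

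**Working it through.** The plan gives no VAS effect size, scale, unit or power figure, so there is no planned number to reproduce. The check is a comparison of texts followed by a count.

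**1. Sites named for the VAS**

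| Place | VAS site | Limited to a cohort? | Disability index split by region? |
|---|---|---|---|
| 4.2 Objectives | back and leg | no | yes |
| 7.1 Table 1 | back and leg | no | yes |
| 7.2.1 Screening | back and leg | no | yes |
| 7.2.3 Follow-up | back and leg | no | yes |
| Synopsis | none | no | ODI/NDI named together |
| 10 Outcome Measures | none | no | ODI/NDI named together |

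Of the places that name a site, 4 of 4 say back and leg, and 0 of 4 say neck or arm.

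**2. Could back be read to include the neck?** The protocol's own questionnaires suggest not. The ODI instructions (Appendix 5) ask about back or leg pain, and the NDI instructions (Appendix 6) ask about neck pain. Back and leg is therefore the lumbar pair in this document's own usage.

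**3. Number of assessments affected**

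- Cervical cohort cap (Section 12.1): 50.
- VAS time-points (Table 1): baseline, 6 months, 12 months = 3.
- Upper bound: 50 × 3 = **150** assessments, with no attrition.

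Section 5.1 also expects about 200 subjects in total, which conflicts with two caps of 50 (50 + 50 = 100). If 200 were meant and split equally, which is an assumption, the bound would be 100 × 3 = 300. Because of this conflict, no share of the whole study is given.

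**4. How much the NDI recovers**

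- Sections worded in terms of pain: 1, 2, 3, 4, 8 and 10, so 6 of 10.
- Sections naming neck pain: 4, 8 and 10, so 3 of 10.
- Sections naming arm pain: 0 of 10.

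Section 1 is a direct six-level rating of pain intensity, and the NDI is collected from ACDF subjects at the same three time-points. Some information on change in neck pain therefore survives. A stand-alone neck pain VAS and any measure that names arm pain do not.

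**The case against.** The strongest objection is that the plan never says in words that every subject rates back and leg pain. The lists only lack a qualifier, and the authors may have meant that pair for lumbar subjects and left the cervical site unstated. This reading is possible, but unqualified lists of what must be collected apply to everyone on their plain meaning, and the neighbouring line shows that the authors divided instruments by region when they intended to. If the other reading were right, the cervical cohort would have no stated VAS site, which also needs correcting.

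The second objection is that Appendix 7 may carry neck and arm scales. This stands as a limit on the consequence. In that case no assessment need be lost, and the defect is that four sections contradict the form.

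Third, the NDI mitigates more than its section counts suggest, because its opening instruction frames the whole questionnaire around neck pain and Section 1 rates intensity directly. That is fair, and it is one reason the point is not graded higher. It does not supply arm pain or a VAS.

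Finally, no readable section mentions arm pain, so the documents alone establish only that a cervical site must be stated. Neck and arm is proposed here as the counterpart of the trunk-and-limb pair used for lumbar subjects, and the sponsor should confirm it.

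**Conclusion.** The concern holds. As written, the cervical VAS change would be measured on regions the surgery did not treat. It affects one of four listed secondary outcomes, in one of two separately analysed cohorts, up to 150 assessments at the Section 12.1 cap.

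The mismatch in wording is certain. The number of assessments actually affected assumes that sites follow the four sections as written and that Appendix 7 does not already provide cervical scales. No size of lost effect can be given. The primary fusion outcome is unaffected, and Section 12 plans descriptive statistics only, so this should be fixed but does not undermine the study's main purpose.

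**What to change.** In Sections 4.2, 7.1 (Table 1), 7.2.1 and 7.2.3, and in the synopsis and Section 10 where no site is given, write: *VAS back and leg pain (lumbar fusion) or VAS neck and arm pain (cervical fusion)*. Check Appendix 7 and the eCRF and align both with that wording. Report the cervical VAS change on neck and arm pain.

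If ACDF subjects have already been enrolled without a neck and arm baseline, count them, report the number, and leave them out of the cervical VAS change. Any back and leg scores they gave can be listed separately under that label.

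The cost is a wording change in six readable places, plus the appendix and one eCRF form if they lack cervical scales. It needs a protocol amendment, with IRB review where Section 15 requires it, and adds no visit or procedure. The drawback is a smaller denominator for the cervical VAS change if subjects were enrolled before the correction.
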